Title: A Study to Test the Effectiveness of Different Interventions to Improve Physical Activity in Adults.

NCT Number: NCT04902014

Document Date: 9/8/2022

Background

Physical Activity (PA) and Health

According to the Centers for Disease Control and Prevention (CDC), adults (≥ 18 years) should participate in at least 150 minutes (two hours and thirty minutes) moderate-intensity physical activity (MPA) per week, or 75 to 150 minutes of vigorous intensity physical activity (VPA) per week, or some combination of both.¹ This level of PA is associated with substantial health benefits including improvements in cardiovascular health, muscular fitness, and cognitive function.¹ More than two thirds of U.S. adults do not meet these guidelines and have a 67% higher risk for all-cause mortality and contribute to the \$117 billion dollars in health care costs associated with physical inactivity.¹⁴

Self-Determination Theory and Physical Activity

Behavior-change theory-driven interventions and in particular those based in Self-Determination Theory (SDT) have been successful in improving PA participation in a variety of populations, in part due to a focus on intrinsic motivation.^{12,39-43} Behaviors that are intrinsically motivated are undertaken for the sake of the behavior itself; inherent satisfaction is the reward.¹⁰ In contrast, extrinsic motivation is associated with motivation by external factors and at its extreme, motivation by coercion.¹⁰ More autonomous, or intrinsic motivation, is correlated to long-term PA engagement while extrinsic motivation has been shown to be effective in PA initiation, but not sustainability.^{9,17}

Wearable Fitness Trackers to Improve Physical Activity Engagement

A promising tool to enhance PA participation is the use of a wearable fitness tracker (WFT) such as a Fitbit or Apple Watch. The small, relatively low-cost, and user friendly WFTs have been developed to support sedentary or under-active individuals in increasing their PA

engagement.¹⁸ Short term studies have indicated that WFT use increases both self-reported PA and objectively measured PA in adults.^{44,45} However, this improvement is not sustained in a majority of individuals.⁴⁶⁻⁵¹ Furthermore, it is known that most WFT consumers discontinue tracker use within six months of purchase.⁵² Therefore, it continues to be relatively unknown whether or not WFT impact motivation for PA or PA behavior in the long-term.⁵⁰

Multiple Behavior Change Techniques Are Better Than One

One potential method to improve the effectiveness of WFTs is to combine them with other interventions. According to a review by Sullivan and Lachman,¹³ the most effective strategy to increase PA and sustain that increase is to employ multiple behavior change techniques. Several studies have combined wearable tracker use with other interventions such as cash incentives for hitting goals,⁴⁸ challenges sent to participants via email,⁴⁷ and a mobile application loaded with an exercise program.⁴⁴ Specifically, we propose combining WFT use with a Self-Determination theory driven Motivational Interviewing (MI) intervention to improve PA motivation and engagement.

Motivational Interviewing and Physical Activity

MI is a person-centered form of engagement that encourages people to assess their own position on the motivation continuum, explore the reasons behind their position, and determine how to best shift from amotivation or ambivalence to a more autonomous position. While MI was not developed with SDT in mind, Deci & Ryan⁵³ point out that SDT and MI have historically been congruent, particularly with their emphases on autonomy support to make health-related decisions and changes. Specifically, both SDT and MI are focused on the central ideal of motivation and the development of internal motives, and the exposure and consideration of externally imposed goals or pressures to act which have no personal meaning to the

individual.⁵⁴ SDT constructs and MI, both on their own and combined, are effective in improving both motivation for PA and PA behavior in a range of age groups. A number of studies measuring changes in PA in response to an SDT-based intervention or MI, or a combination of the two saw statistically significant increases in PA.^{39,43,55-58} Research has also indicated that SDT-based MI is a powerful intervention to shift motivation for PA from mostly extrinsic to mostly intrinsic.^{39,59,60}

WFTs and MI: A Powerful Combination

Two pilot studies^{61,62} found that combining SDT-based MI interventions with wearable tracker use significantly improved self-reported PA, body weight, and HDL cholesterol in African American men⁶¹ and increased the likelihood of meeting daily step goals in adolescent-parent dyads.⁶² These results present an encouraging possibility for improving PA in sedentary adults: WFTs and SDT based MI. Given the popularity of wearable fitness trackers and the effectiveness of SDT based MI in increasing PA motivation and behavior, the combination of the two shows promise to improve the overall health of adults. Therefore, the purpose of this study is to assess the impact of a self-determination theory motivational interviewing intervention in combination with wearable fitness tracker use on motivation for PA and PA behavior.

Methods

Participant Recruitment and Health Screening

Participants aged 18 and over will be recruited through a variety of means including flyers on the Colorado State University campus, flyers in local fitness centers, physician referrals, social media, and mass emails. In order to detect difference between groups with 95% confidence in repeated measures analyses, we will seek to recruit 40 total participants in order to allow for attrition. We aim to have 32 participants complete the study. To be included in this

study, participants must be over the age of 18 and must not meet physical activity guidelines of at least 150 minutes of moderate physical activity per week. They must own an Android or iPhone smartphone device and be willing to download a mobile application onto that device for use during the intervention. They also must be willing to potentially wear a WFT and/or attend bi-weekly remote MI. Participants must not have a history of heart disease or diabetes, and must not have limiting conditions like concurrent cancer treatment, peripheral artery disease, orthopedic injury, or pain limiting arthritis. They must also not seek to participate in other structured PA programs for the duration of the study, must not be pregnant or seek to become pregnant, and must not have been diagnosed with alcohol or substance abuse during the previous twelve months.

After having established the eligibility of a potential participant via a screening form, participants will be consented and will complete baseline assessments. This session will involve the administration of all self-reported measures, as well as instruction on accelerometer use. Participants will wear the accelerometer for the subsequent 7 days to provide baseline data on their baseline level of PA. Researchers will collect the ActiGraphs after the 7-day period.

Participants who complete the baseline PA assessment will be invited to a remote session to receive general physical activity guidelines education and will take approximately 1 hour. Prior to this meeting, participants will have been randomly assigned to one of the four study groups (i.e., WFT, MI, WFT+MI, or PA Education Control) using a randomized number generator. To control for age and sex, participants will be age- and sex-matched in each group. During this remote meeting, participants will be informed as to which group they have been randomized into.

Description of Intervention:

The duration of the study will be twelve weeks. The four study conditions are as follows:

WFT: Individuals assigned to this experimental condition will be given a wrist-worn WFT and will be instructed to wear it for the duration of the study. They will also be instructed to download the corresponding mobile application on their smartphones to be used for the duration of the study. They will be trained by a member of our team on how to utilize the WFT and mobile application. The intended WFT tracks daily steps, miles traveled, kcals expended, and daily activity time. This device provides these data to the wearer via a small screen. Participants will be instructed to try and complete at least 150 minutes of PA per week. Researchers will have the capability to track participant daily PA via the WFT mobile application account created for each participant. These individuals will be asked to set biweekly PA goals, which will be emailed to the study coordinator. These participants will also receive general physical activity guidelines education and information on strategies to reach the recommended amount of activity per week during the initial baseline assessment meeting. Participants in this condition will be asked to ONLY wear the WFT provided to them by researchers.

MI: The individuals will be scheduled for and participate in six biweekly remote SDT based MI sessions. These sessions will take place via video calling platforms like Microsoft Teams, Zoom, or Skype. The MI sessions will be conducted by a PhD student who has been trained by a MI practitioner. Participants will be provided a log book and will be asked to log their PA, with the goal of completing at least 150 minutes of PA per week. These participants will also receive general physical activity guidelines education and information on strategies to reach the recommended amount of activity per week during the initial baseline assessment meeting. Participants in this condition will be asked to NOT wear a WFT of their own over the course of the intervention.

WFT+MI: These individuals will be given the wrist-worn WFT, be instructed to wear it for the duration of the study AND be scheduled for six SDT based remote MI sessions. These participants will also be trained by a member of our team on how to utilize the WFT and associated application. They will be instructed to try to complete 150 minutes of PA per week. Researchers will have the capability to track participant daily PA via the WFT and associated API. These participants will also receive general physical activity guidelines education and information on strategies to reach the recommended amount of activity per week during the initial baseline assessment meeting. Participants in this condition will be asked to ONLY wear the WFT provided to them by researchers.

PA Education Control: These participants will receive general physical activity guidelines education and information on strategies to reach the recommended amount of activity per week during the initial baseline assessment meeting. Participants will be asked to NOT wear a WFT of their own over the course of the intervention. At the conclusion of the study, these participants will be offered the chance to participate in one MI session.

Outcome measures: The following outcome measures will be collected at baseline, and at the completion of the twelve-week intervention.

- **Objectively measured PA engagement:** PA will be objectively measured by one week of actigraphy using the ActiGraph wGT3-BT activity monitor. Participants will be given the ActiGraph and will be instructed to wear it on a provided elastic belt on their non-dominant hip for one week. They will be given a log to record times that they removed the ActiGraph, which should only be when showering, bathing, or otherwise coming into contact with water. At the conclusion of the week, the ActiGraph data will be downloaded using ActivLife software. Daily PA will be assessed via the WFT

application for individuals in the WFT+MI and WFT groups, and via self-report for the MI group.

- **Motivation for PA:** Motivation for PA will be assessed using the Behavioral Regulation in Exercise Questionnaire (BREQ-3). This instrument is one of the most widely used in PA and exercise motivation research and has been validated in this population.^{21,22} This survey will be accessed via a secure online link.
- **Covariates:** Each of the following covariates will be collected pre-intervention: age, race/ethnicity, education level, family affluence, and height/weight (BMI). All, except height and weight will be collected with self-report. Height and weight will be measured by lab personnel during the first visit to the lab.

Data Analysis

Means and standard deviations of the following variables will be calculated: baseline and follow-up MVPA, steps, and energy expenditure, baseline and follow-up scores for PA motivation subscales, and participant age and BMI. Paired t-tests will be used to compare within subjects pre-participation values from post-participation values for PA, and motivation variables by group. ANCOVA will be used to compare between subjects differences in outcome variables by group. Models will be developed based on covariate correlation with outcome variables and other covariates.

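### The baseline ActiGraph week has no stated role in balancing the arms and no secured place in the ANCOVA, so chance gaps in baseline activity can carry into the between-arm comparison

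*Combined protocol and SAP*

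**What the plan says.** All places are in the combined protocol and SAP.

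- **Eligibility** (Methods, Participant Recruitment and Health Screening). Participants "must not meet physical activity guidelines of at least 150 minutes of moderate physical activity per week". The check is made on a form, before any device is worn: "After having established the eligibility of a potential participant via a screening form, participants will be consented and will complete baseline assessments".
- **Baseline week** (same section). "Participants will wear the accelerometer for the subsequent 7 days to provide baseline data on their baseline level of PA". The devices are then collected. No threshold, exclusion or balancing role is attached to the reading.
- **Step to assignment.** "Participants who complete the baseline PA assessment will be invited to a remote session". On timing: "Prior to this meeting, participants will have been randomly assigned to one of the four study groups". That assignment follows the ActiGraph week is the natural reading, but it is not stated.
- **Balancing.** "To control for age and sex, participants will be age- and sex-matched in each group". No other factor is named.
- **Outcome** (Outcome measures). "PA will be objectively measured by one week of actigraphy using the ActiGraph wGT3-BT activity monitor", at baseline and again at twelve weeks. The baseline week is therefore the baseline of the objective outcome.
- **Analysis** (Outcome measures; Data Analysis). The listed covariates are age, race or ethnicity, education, affluence and BMI. Baseline activity is not among them. The between-arm method is ANCOVA, with covariates to be chosen from the correlations seen in the data.

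**The concern.** By the time people are assigned, the trial can hold an objective measurement that is both the baseline of its activity outcome and a direct reading of the inactivity criterion. The plan gives it no stated use at that point and does not secure its use later.

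Two things follow. First, baseline activity is likely to predict follow-up activity, yet with small arms its balance is left to chance. If the final ANCOVA lacks the baseline term, a chance gap at baseline shows up as a difference at follow-up. Second, someone who passes the form but records 150 minutes or more on the device can still be randomised, so the sample may be more active than its description implies.

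**Working it through.** **Inputs from the document:** 40 recruited, 32 completing, four arms.

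**Assumptions:** equal arms (10 assigned and 8 completing per arm; no ratio is stated), baseline MVPA normal and in SD units, and baseline–follow-up correlation ρ of 0.3 to 0.7. The document gives no SD, correlation, effect size or power.

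**1. The plan's own figure.** 32/(1 − 0.20) = 40, so 40 and 32 agree with 20% attrition. The 32 itself cannot be re-derived. For scale, at 8 per arm, two-sided 0.05 and 80% power, the detectable pairwise difference is (1.96 + 0.84) × √(2/8) = 1.40 SD.

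**2. Chance imbalance at assignment.** The SD of a difference between two arm means is √(2/10) = 0.447.
- A given pair: P(|difference| > 0.5) = 2[1 − Φ(0.5/0.447)] = 26%. At 8 per arm the SD is 0.5 and the figure is 32%.
- Any two of the four arms (simulated range of four means > 0.5): 68%. If age and sex matching removes 10% or 20% of the variance: 64% or 59%.

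**3. What a gap does if unadjusted.** Shift in a follow-up-only comparison = ρ × gap. For a 0.5 SD gap: 0.3 × 0.5 = 0.15 SD, up to 0.7 × 0.5 = 0.35 SD.

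**4. What the baseline covariate gives.** Variance of an 8 v 8 difference, with one slope fitted across all four arms:
- Unadjusted: 2/8 = 0.25.
- With baseline in the ANCOVA: 0.25 × (1 − ρ²) × (1 + 1/26), where 26 = 32 − 4 − 2. For ρ = 0.5 this is 0.195, a 22% reduction. For ρ = 0.7 it is 0.132, a 47% reduction.
- Perfect balance could then save at most 1 − 1/(1 + 1/26) = 3.7%. In simulation an ideal median split moved the variance from 0.193 to 0.191 (ρ = 0.5) and from 0.132 to 0.130 (ρ = 0.7), that is 1.0% and 1.5%.

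**5. What balancing gives.** An exact median split (5 below and 5 above in every arm) cuts the 68% to 25 or 26%, but it needs all 40 values before anyone is assigned. A workable scheme is minimisation on three binary factors with an 80% preferred assignment. Its simulated chance that some two arms differ by more than 0.5 SD, as a range over several simulations, is:

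| Cut for baseline MVPA | Chance of a gap > 0.5 SD |
|---|---|
| Baseline not used | 66–68% |
| Median | 35–40% |
| 70th percentile | 42–45% |
| 90th percentile | 59–62% |

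If 10 to 30% of eligible people exceed 150 minutes (an assumption), a cut at 150 lies at the 70th to 90th percentile, where much or most of the benefit is lost.

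**6. People already at target.** If a share q passes the form, the chance of at least one among 40 is 1 − (1 − q)^40: 55% at q = 2%, 87% at 5%, 98.5% at 10%. The document does not give q.

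**The case against.** The strongest reply is that ANCOVA already deals with chance imbalance, so balancing on baseline activity is a matter of taste. On precision this largely stands: with baseline in the model, balancing adds only about 1% in simulation. But the plan does not commit to that model. Baseline activity is missing from the covariate list, and selection by observed correlation leaves its inclusion open. The main repair is therefore in the analysis section, with balancing as a cheap addition.

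It is also fair to say that form-based eligibility is a legitimate choice. One week of accelerometry is noisy, and excluding people on it has a cost: to randomise 40, about 40/(1 − q) people must wear the device, that is 45, 50 or 58 for q = 10%, 20% or 30%.

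A reader might infer three stronger points that the document does not support.

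- *That active people are in fact randomised and the effect is diluted by a known amount.* If a share q did not respond at all, 32 completers would be worth 32(1 − q)², or 25.9, 20.5 and 15.7 at 10%, 20% and 30%. But q is unknown, and zero response is an assumption. The 150 minutes given to participants is a minimum, and nothing says that MVPA, steps or energy expenditure stop responding there. For the motivation subscales the argument has even less footing.
- *That the randomisation is biased.* It is not. The gaps described here arise by chance.
- *That those at or above 150 minutes must be excluded.* This is a trade-off, not a correction of an error.

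**Conclusion.** The concern holds as a gap in design and analysis wording. The plan measures the baseline of its objective outcome, on the natural reading before assignment, but does not use it for balance and does not guarantee it a place in the ANCOVA. With 10 per arm, a gap above 0.5 SD between some two arms is expected in about two thirds of draws, and in 26% for a given pair. Without a baseline term, such a gap moves the follow-up comparison by 0.15 to 0.35 SD. These figures rest on equal arms, normality and the assumed correlations.

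That people already at 150 minutes can be randomised follows from the text. How many, and with what loss of effect, does not.

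**What to change.** 1. **Order.** State that assignment takes place after the baseline week has been downloaded and scored.
2. **Covariate.** Pre-specify the baseline value of each outcome as a covariate in its between-arm ANCOVA, whatever correlations are observed. This is one sentence and brings most of the gain.
3. **Balance.** Add baseline MVPA to age and sex as a minimisation factor with a random element. Fix the cut in advance, near the expected median of eligible participants and not at 150 minutes.
4. **Eligibility.** Keep the form and describe inactivity as self-reported. Optionally pre-specify a sensitivity ANCOVA in those below 150 minutes on the baseline week. At assumed shares of 10 to 30% above target it would hold about 29 to 22 completers (32 × 0.9 = 28.8; 32 × 0.7 = 22.4). The subset is defined before assignment, but dropout afterwards can still bias it.

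**Cost.** No new procedure is needed, since the device is already worn and collected. The data must be scored before assignment. That means fixing intensity cut-points and a valid-wear rule first, which the Outcome measures section does not give. The document offers no figure for the expected median, so the cut must be justified from elsewhere, and a poor choice shrinks the balancing benefit as the table shows.

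### The allocation is drawn before the education session shared by all four arms, so that session can be delivered with the arm known; its timing is also stated in two conflicting ways.

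*Combined protocol and SAP*

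**What the plan says.** The recruitment section of the Methods starts with screening, consent and a baseline session, of which it says "This session will involve the administration of all self-reported measures, as well as instruction on accelerometer use". Seven days of accelerometer wear follow. Then: "Participants who complete the baseline PA assessment will be invited to a remote session to receive general physical activity guidelines education". The session lasts about an hour.

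On allocation, the same section says "Prior to this meeting, participants will have been randomly assigned to one of the four study groups", made "using a randomized number generator". It adds "To control for age and sex, participants will be age- and sex-matched in each group", without saying how. On disclosure it says "During this remote meeting, participants will be informed as to which group they have been randomized into". Whether disclosure comes before or after the teaching is not stated.

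The arm descriptions under Description of Intervention time the education differently. All four use the same phrase: "recommended amount of activity per week during the initial baseline assessment meeting".

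For controls, the education is the only component during the twelve weeks; one motivational interviewing (MI) session is offered to them once the study is over. No script, allocation-blind educator or concealment of the drawn assignment is described. The Data Analysis section names no analysis population.

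**The concern.** The education is meant to be the constant part of the design. Each active arm is education plus a tracker, MI or both, and control is education alone. A contrast with control isolates the added component only if the education is the same on both sides.

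On the recruitment section's account, the assignment exists before the teaching starts. Staff who know it could put more or less effort into the hour according to arm. A participant who hears the assignment first could be more or less receptive. The content includes strategies for reaching the recommended activity level, and motivation is measured by self-report (BREQ-3), so effort and receptiveness could plausibly matter.

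The same order means that a person who does not attend is already in the randomised set, although drawing after the teaching would have kept that person out of it.

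**Working it through.** **1. The two accounts side by side**

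| Question | Education in the remote session (recruitment section) | Education in the first baseline meeting (arm descriptions) |
|---|---|---|
| Is the draw before the education? | Yes | Not stated; the draw is only said to precede the remote session |
| Could the educator know the arm? | Yes, nothing prevents it | Only if the draw was made before that meeting |
| Could the participant know the arm? | Only if disclosure precedes the teaching within the hour | No, disclosure comes later |
| When is baseline accelerometry? | Before the education | After the education |

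The concern about arm-aware teaching belongs to the first column. In the second it largely falls away, but baseline activity would then be recorded after the education. The first account is the more specific, since it gives the session's purpose and length. On that account the baseline questionnaires and accelerometry are complete before disclosure, so disclosure cannot affect them.

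**2. Bias from arm-aware education**

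Let e(A) and e(C) be the effect of the education as delivered in an active arm and in control. The contrast with control estimates

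added-component effect + [e(A) - e(C)].

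The bracket is zero if the education is identical. The documents give no figure for it and no basis for its sign, so it cannot be computed.

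**3. People who miss the session**

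Inputs from the recruitment section: 40 to be recruited and 32 to complete. The allowance is 40 - 32 = 8, and 8/40 = 20%. That 20% is back-calculated, because no dropout rate is stated. The 32 cannot be reproduced, because no effect size, standard deviation (SD) or power is given. The no-show rate q is an assumption.

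| q | No-shows, q x 40 | Further losses before completers fall below 32 | As a share of those remaining |
|---|---|---|---|
| 0% | 0 | 8 | 8/40 = 20% |
| 5% | 2 | 6 | 6/38 = 15.8% |
| 10% | 4 | 4 | 4/36 = 11.1% |
| 20% | 8 | 0 | 0/32 = 0% |

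From 0% to 10%, no-shows use 0 to 4 of the 8, that is, none to half of the allowance.

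**4. What that means for precision**

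Further assumptions: equal allocation (no ratio is stated), so 10 per arm; an unadjusted two-sample t-test; two-sided alpha 0.05; 80% power. Solve for d where a noncentral t with 2n - 2 degrees of freedom and noncentrality d x sqrt(n/2) gives power 0.80.

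- n = 10 per arm: d = 1.32 SD
- n = 9 per arm (4 no-shows spread evenly): d = 1.41 SD
- n = 8 per arm (the planned 32 completers): d = 1.51 SD

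Four no-shows followed by four later losses end at the planned 8 per arm. ANCOVA with a useful baseline covariate would lower all three values.

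**The case against.** Three stronger readings are tempting, and the documents do not support them.

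- A reader might infer that the order biases every contrast with control. Disclosure after the teaching also fits the text. The documents do not say who teaches, whether that person holds the assignments, or whether sessions are individual or grouped. The order permits bias; it does not establish it.
- A reader might infer that non-attenders are lost and receive nothing. No rule drops them or bars rescheduling. Tracker hand-over, device training and MI scheduling are not tied to this session, so a non-attender in an active arm could still be treated, followed up and analysed as assigned.
- A reader might infer that no-shows unbalance the arms systematically. Participants learn their arm only at the session, so staying away cannot be their reaction to it. Expected loss is the same across arms unless staff who know the allocation pursue attendance differently. Chance imbalance remains.

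It can also be said that arms are known through twelve weeks of trackers or MI, so one more unblinded hour adds little. That limits the likely size of the problem. It does not justify leaving the shared component exposed when a change of order would protect it.

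The strongest objection is that the protocol contradicts itself on when the education happens. That stands in full and is part of the point: the order is not settled until the two accounts are reconciled. The missing analysis population also stands, as a separate gap that reordering the session does not fill.

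**Conclusion.** The point holds as a defect of sequence. On the recruitment section's account, the draw precedes the shared education and nothing described keeps the assignment from whoever delivers it. The possible bias in contrasts with control cannot be sized or signed from the documents. The cost of no-shows is mainly precision: 0 to 4 people if 0% to 10% of 40 is assumed, inside the allowance of 8.

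This rests on the recruitment section's timing being the intended one. If the arm descriptions govern, the concern about arm-aware teaching largely falls, and the placing of education before baseline accelerometry has to be addressed instead. Either way the protocol needs one statement of timing. The change is worth making because it is cheap and replaces a stated order, not because harm has been shown. Confidence is medium.

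**What to change.** 1. State one timing for the education, after the seven days of baseline accelerometry, and align the recruitment section and all four arm descriptions with it.
2. In the remote meeting, deliver the education to all attenders first.
3. Then draw the assignment. If age and sex matching needs preparation in advance, open a concealed assignment at this point instead.
4. Disclose the arm at the end of the same meeting, with device training and MI scheduling afterwards.

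Keep the recruitment target at 40. Redefining it as 40 randomised attenders would mean consenting more people whenever someone fails to attend. The change does not recover no-shows; it keeps them out of the randomised set.

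The cost is protocol wording, a small change in running order and a concealment step. If assignments are prepared in advance and only opened at the end, the matching must allow for people who do not attend and whose assignments stay unopened. The documents do not say when trackers are handed over, so any effect on that step is for the sponsor to check.

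### Arms are to be matched on age and sex, but the ANCOVA plan leaves sex off the covariate list and lets age in only if its observed correlation selects it

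*Combined protocol and SAP*

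**What the plan says.** The paragraphs on allocation, under Participant Recruitment and Health Screening, assign participants to four groups "using a randomized number generator" and add: "To control for age and sex, participants will be age- and sex-matched in each group". No strata, age bands, matched sets or minimisation rule are described. The same section gives the planned size: "We aim to have 32 participants complete the study", out of 40 recruited.

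The Covariates item under Outcome measures states: "Each of the following covariates will be collected pre-intervention: age, race/ethnicity, education level, family affluence, and height/weight (BMI", and the list ends there. Age is on it; sex is not.

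Data Analysis gives the between-group method in one sentence: "ANCOVA will be used to compare between subjects differences in outcome variables by group". The only rule on model terms is the next one: "Models will be developed based on covariate correlation with outcome variables and other covariates". No covariate is fixed in advance and no entry threshold is given. Sex is not mentioned in that section.

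**The concern.** The sponsor names age and sex as the two factors to be controlled and acts on both at allocation. The analysis then treats one as optional and does not name the other.

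Balancing arms on a prognostic factor removes that factor's contribution from the true variability of the difference between arms. A model without the factor still puts its variance into the residual. The estimated standard error is then larger than the true one, the test rejects too rarely under the null, and part of the precision bought by matching is given away. There is no bias and no inflated type I error. What is at stake is power, and with about 32 completers over four arms the trial has little to spare.

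If the matching is not achieved, this conservatism disappears. Fixed age and sex terms are then ordinary covariate adjustment, worthwhile only if the two factors explain enough variance to repay two degrees of freedom and some chance imbalance.

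**Working it through.** **The plan's own figures.** 40 and 32 agree with each other at an implied attrition of 1 − 32/40 = 20%, since 32/(1 − 0.20) = 40. The basis for 32 cannot be reproduced, because no effect size, SD, power or correlation is given. With equal allocation (assumed), 32/4 = 8 completers per arm.

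**Direction and upper limit.** Let R be the share of the variance left after baseline that age and sex explain together, with that variance set to 1. With exact matching, the true variance of a pairwise difference is about (2/8)(1 − R). A model omitting both factors estimates about 2/8. The ratio of estimated to true variance is about 1/(1 − R): 1/0.90 = 1.11 at R = 10% and 1/0.80 = 1.25 at R = 20%. The plan's rule falls below these values because age is sometimes entered.

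**Simulation inputs (all assumed; none is in the documents).**
- Four arms of 8, baseline–outcome correlation 0.5, baseline term in the model, two-sided 5% test of one pairwise contrast of 1.2 residual SD.
- Age and sex equally prognostic.
- Matched arms: 8 sets of four people of the same sex and nearly the same age (within-set age SD 0.15 of the between-set SD), one per arm. Unmatched arms: simple random allocation to equal arms.
- Plan's rule: age enters if its correlation with the outcome has p<0.05; sex never enters. Comparator: age and sex always in the model.
- 40,000 runs per setting; Monte Carlo error about 0.25 points on power and 0.11 on type I error.

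**Matched arms, plan's rule vs fixed terms.**

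| R | Type I error (%) | Power (%) | Power gain from fixed terms |
|---|---|---|---|
| 0% | 5.0 vs 4.9 | 62.6 vs 61.8 | −0.8 |
| 5% | 4.7 vs 5.0 | 63.4 vs 64.2 | +0.8 |
| 10% | 4.3 vs 5.0 | 63.8 vs 66.3 | +2.5 |
| 20% | 3.6 vs 4.9 | 66.0 vs 71.2 | +5.2 |

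Under the plan's rule the estimated variance is about 7–8% too large at R = 10% and 15–16% too large at R = 20%. Age is selected in only 14% and 26% of runs respectively, so the rule usually drops age even when it matters.

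**Unmatched arms.** Type I error under the plan is 5.0% to 5.3%. Power, plan vs fixed: 61.8% vs 58.9% (R = 0), 61.9% vs 61.1% (5%), 61.9% vs 63.0% (10%), 63.1% vs 68.8% (20%).

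**Sensitivity, matched arms.**
- Entry at p<0.20: plan's power 64.6% (10%) and 67.0% (20%), with age selected in 36% and 51% of runs.
- No baseline term (R is then a share of total variance): 65.8% vs 68.1% and 68.4% vs 73.0%.
- Contrast of 1.0 SD: 48.7% vs 51.3% and 49.3% vs 55.3%. Contrast of 1.5 SD: 82.7% vs 84.4% and 85.2% vs 88.5%.
- 40 matched, 32 retained at random (20,000 runs): 61.8% vs 60.7% (R = 0), 62.5% vs 64.9% (10%), 64.7% vs 69.8% (20%).
- A separate simulation used the overall four-group F-test, no baseline term and exact balance on sex and two age bands, with one arm shifted by 1.2 SD (6,000 runs for type I error, 3,000 for power). At 20% it gave type I error 2.9% vs 4.9% and power 65.5% vs 73.1%.

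**The case against.** The strongest reply has four parts.

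*The loss is small and rests on an assumed prognostic strength.* This stands. Below about 5% of variance there is nothing material to recover, and a baseline activity term may already absorb part of what age and sex explain; the simulation draws baseline independently of both.

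*The conservatism requires the matching to succeed, and the protocol gives no mechanism for it.* This also stands. With unmatched arms the plan's rule does better at 0% and 5%, and fixing the terms costs about 3 points if the factors are uninformative. The change is close to free only when matching works.

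*Sex must be known in order to match on it, and the list of covariates to be collected need not be closed for modelling, so sex could still be a candidate.* Its omission may well be an oversight. In separate matched-arm runs with sex allowed in under the same correlation rule, power against fixed terms was 64.8% vs 66.0% (10%) and 69.1% vs 71.2% (20%) with entry at p<0.05, and 66.3% vs 66.1% and 69.7% vs 70.5% with entry at p<0.20. Listing sex therefore recovers much of the loss, and nearly all of it under the looser threshold. But the plan states no threshold, and as written it neither lists sex nor puts it in a model.

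*The form of adjustment depends on the matching method.* This is fair. If strata or matched sets are used, terms for those may be preferable, which is a reason to describe the method in the same edit. The open selection rule for the other covariates, and the absence of a named baseline term, are wider gaps that this point does not settle.

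**Conclusion.** The point holds. Allocation and analysis are not aligned: of the two factors chosen for control, one is missing from the covariate list and the other enters only by selection. The consequence is conservatism and a modest loss of power, with no bias and no inflation of type I error. With matched arms the loss is about 2.5 points at 10% of residual variance and about 5 points at 20%. Across contrasts of 1.0 to 1.5 SD it is 1.7 to 2.6 points at 10% and 3.3 to 6.0 at 20%. It is negligible at 5% and slightly reversed at 0%.

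These sizes depend on equal arms of 8, on the matching being achieved and on assumed variance shares, so confidence in the magnitude is medium. The mismatch in the text does not depend on any of them. It should be corrected, but it does not threaten the validity of the comparison.

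**What to change.** Add sex to the Covariates list. In Data Analysis, state that age and sex are fixed terms in every between-group ANCOVA, whatever their observed correlations. In the allocation paragraph, state how the number generator and the age and sex matching are combined, as a clarification; if strata or matched sets are used, say whether terms for these take the place of age and sex.

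The cost is a few sentences and two residual degrees of freedom: with 32 completers and a baseline term, 32 − 4 − 1 = 27 falls to 25. If age and sex explain nothing, the power cost is under 1 point with matched arms (62.6% to 61.8%), about 1 point after random dropout from 40 to 32 (61.8% to 60.7%), and about 3 points if the matching is not achieved (61.8% to 58.9%). Recruitment, visits and interventions are unchanged.
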